5.3.2.3.4. Percent Change of Brain Volume from Baseline

PCBV from Core Baseline to Extension EOT will be summarized using descriptive statistics by visit based on observed data and listed using the FAS and EXTS.

PCBV from Core study EOT to Extension EOT will be summarized using descriptive statistics by visit based on observed data and listed using the EXTS.

Number and percentage of subjects with annual change from Core Baseline to Extension EOT in PCBV <= -0.4% will be summarized by visit using EXTS.

Number and percentage of subjects with annual change from Core study EOT to to Extension EOT in PCBV <= -0.4% will be summarized by visit using EXTS.

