5.3.1.2.1. T1 Gd+ lesions

The following variables are derived at each scheduled visit during the Combined Analysis Period:

- Total number of T1 Gd+ lesions, derived as:
 Number of new T1 Gd+ lesions (T1GdNewR) + number of persisting T1 Gd+ lesions (T1GdR);
- Total number of T1 Gd+ lesions, categorized (0, 1, 2, 3, 4, 5, 6-10, 11+).

In addition, the following analyses will be conducted:

- The cumulative number of Gd+ T1 lesions from core baseline to extension EOS and corresponding number of scans included will be used as derived.
- Absence of Gd+ T1 lesions at each visit: 'Gd+ T1 lesions at each visit' are considered 'absent', if the number of Gd+ T1 lesions at each visit is zero. If > 0 they are considered 'present'. This applies to nominal visit collected in the CRF.
- Absence of Gd+ T1 lesions from Core baseline until extension EOS: Absence of new Gd+ T1 lesions from Core baseline to extension EOT (including all unscheduled scans) is defined 'absent' if the 'number of new Gd+ T1 lesions' at all post-baseline MRI scans up to the extension EOS is zero. This includes all scheduled and all unscheduled visits. If > 0 at any visit it is considered 'present'. The corresponding 'Number of MRI scans' and time to last MRI scan are derived. If no MRI result at the visit is available (based on visit window), the information is considered missing (for lesion free subjects).
- Total volume of T1 hypointense lesions and the change from baseline: Total volume of T1 hypointense lesions (mm3) (variable T1BHVOL) is recorded by the central reader at each visit. The change from Core baseline is derived as the change from total volume of T1 hypointense lesions at Core study Visit 2-Baseline. The change from Extension baseline is derived as the change from last available record of total of T1 hypointense lesions prior to Extension Baseline.
- Proportion of Gd+ T1 lesions at Core Baseline evolving to persistent black holes (PBHs): It is the proportion (%) of 'Number of T1 hypointense lesions (persistent black holes) evolved from T1 Gad.-enhancing lesion at V2 Baseline core study' (variable T1BHV2C) at each scan visit out of the 'Number of Gd+ T1 lesions at Core baseline'.

Note: Gd+T1 lesions are assumed to not enhance for more than 12 weeks. This requires handling of data as follows:

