5.3.1.2.4. Percent Change of Brain Volume from Baseline

Brain volume is recorded by the central reader as normalized brain volume at the baseline visit and at subsequent visits as a percent change relative to the value at the baseline visit. Percent change of brain volume from baseline to subsequent visits is not manually derived but taken directly from the central reader variable at the corresponding scheduled visit.

The following types of percent change of brain volume are assessed in the extension study:

- Percentage change of Brain Volume from Core Baseline
- Percentage change of Brain Volume from Extension Baseline, i.e. from Core study EOT
- Annual percentage change of Brain Volume from Core Baseline to Core study week 108, defined as: percentage change of MRI brain volume assessment at core study week 108 relative to Core baseline / years-of-follow-up. Here the years-of-follow-up is: (Date of MRI brain volume assessment at core study week 108 – randomization date in core study +1)/ 365.25
- Annual percentage change of Brain Volume from Core Baseline to extension EOS, defined as: percentage change of last MRI brain volume assessment relative to Core baseline / years-of-follow-up. Here the years-of-follow-up is: (Date of last MRI brain volume assessment in extension study – randomization date in core study +1) / 365.25.

CONFIDENTIAL - FOIA Exemptions Apply in U.S.

Annual percentage change of Brain Volume at any assessment by visit from Core Baseline to extension EOS, defined as: percentage change of last MRI brain volume assessment by visit relative to Core baseline / years-of-follow-up. Here the years-of-follow-up is: (Date of last MRI brain volume assessment of the visit in extension study – randomization date in core study +1) / 365.25.

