5.3.1.4.2. NEDA-4 status up to extension EOS

No evidence of disease activity (NEDA)-4 up to EOS is defined by the absence of confirmed relapse, Gd+ T1 lesions, new or enlarging T2 lesions, 12-week CDA until EOS, and absence of

annual brain volume decrease $\geq 0.4\%$ at all assessments from Core Baseline up to Extension EOS. If at least one of the criteria is not fulfilled or the subject discontinues treatment prematurely, the subject is not considered to have achieved NEDA-4.

Derivation is as for NEDA-3, but in addition a subject is considered as having evidence of disease activity if the following applies:

• Annual brain volume at any assessment from core baseline to extension EOS decrease ≥ 0.4%. The annual brain volume change is defined in Section 5.3.1.2.4. If at any visit the percentage change is <= -0.4% then the criteria "Annual brain volume decrease ≥ 0.4%" is met

5.3.1.4.3. Change in Multiple Sclerosis Functional Composite (MSFC) Z-score from baseline by visit up to Extension EOS

The Multiple Sclerosis Functional Composite (MSFC) score consists of 3 clinical examinations: Timed 25-Foot Walk, 9-Hole Peg Test (9-HPT), and Paced Auditory Serial Addition Test (PASAT-3" version). The timed 25-foot (7.62 meters) walk is a quantitative measure of lower extremity function. The 9-HPT is a quantitative measure of upper extremity (arm and hand) function. The PASAT is a measure of cognitive function that specifically assesses auditory information processing speed and flexibility, as well as calculation ability.

MSFC will be assessed at pre-randomization (3 tests conducted on 3 days apart, where the first 2 are considered practice tests) and at post-baseline Visits as scheduled in the protocol.

For each assessment, the MSFC score will be calculated as the mean of the Z-scores of the 3 components:

- (1) Timed 25-Foot Walk (T25FW) score (s)
- (2) 9-Hole Peg Test (9-HPT) score (s)
- (3) Paced Auditory Serial Addition Test (PASAT-3) score (Number correct).

Details for generating the MSFC Z-score and how to handle missing data are given in Section 6.14.1.

For analysis, baseline and nominal post-baseline visits are considered. See Section 5.1.10 for remapping of premature end of treatment or unscheduled visits (includes unscheduled visits due to relapse).

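### Annual brain-volume rates run from randomization rather than from the reference scan, and the extension-only annual table has no defined denominator: a small, free improvement

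*SAP*

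**What the plan says.** SAP Section 5.3.1.2.4 takes percent change in brain volume directly from the central reader, relative to the value at the baseline visit. It then defines three annual changes, all from core baseline and all with a clock that starts at core randomization:

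- To core Week 108, years of follow-up use "Date of MRI brain volume assessment at core study week 108 – randomization date in core study +1)/ 365.25".
- To extension EOS, the clock is the same, ending at the last extension scan.
- By visit, "years-of-follow-up is: (Date of last MRI brain volume assessment of the visit in extension study – randomization date in core study +1) / 365.25".

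The change from extension baseline appears only as "Percentage change of Brain Volume from Extension Baseline, i.e. from Core study EOT", without annualization.

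Section 5.3.2.3.4 plans two by-visit counts of subjects at or below -0.4% per year. One is from core baseline. The other is "annual change from Core study EOT to to Extension EOT in PCBV <= -0.4% will be summarized by visit using EXTS".

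Section 5.3.1.4.2 uses the core-baseline rate for NEDA-4: "The annual brain volume change is defined in Section 5.3.1.2.4". A subject meets the brain-volume criterion if the rate is at or below -0.4% at any visit.

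On timing, Section 5.1.3.2 defines the core efficacy baseline as the last value on or before randomization. Section 5.3.1.2.1 labels the core baseline MRI visit in the phrase "change from total volume of T1 hypointense lesions at Core study Visit 2-Baseline". Section 5.1.4 lists core Week 2 as Visit 4.

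**The concern.** An annual rate is a change divided by the time over which it accrued. In Section 5.3.1.2.4 the change starts at the baseline scan and the clock starts at randomization. The scan cannot come later than randomization under Section 5.1.3.2, and the visit numbering suggests that it came at an earlier visit. Where it did, the divisor is too short and annual loss looks larger than it was. The result is then compared with a fixed cut-off. Because NEDA-4 fails a subject on one crossing at any visit, an overstated rate can only add failures.

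The second problem is a missing definition. The count from core EOT needs an annual rate that Section 5.3.1.2.4 does not contain. Two programmers could follow the SAP faithfully and produce different tables.

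**Working it through.** The plan states no figure here that could be reproduced. The check is date arithmetic.

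**Inputs**
- Core Week 60 is taken as Day 421 and core Week 108 as Day 757 (weeks x 7 + 1, the convention of Table 7), counted from randomization.
- Extension Week 48 is extension Day 337, Week 96 is Day 673 and Week 240 is Day 1681 (Table 7).
- The gap from core EOT scan to extension Day 1 is assumed to be 21 days. Sections 1.2.1 and 1.2.2 place follow-up visits 14 to 22 or 23 to 37 days after the last core dose and allow up to 7 days of pre-treatment.
- The lead g, in days from baseline scan to randomization, is **not in the document**. Assumed values are 0, 14 and 45.

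**Core-baseline rates.** For a scan on study day d, the SAP divides by d (the +1 is included), while the time since the scan is d - 1 + g. The computed rate is therefore the scan-based rate times (d - 1 + g)/d. On core-baseline time, extension Week 240 falls on Day 757 + 21 + 1680 = 2458.

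| Visit | d | g = 0 | g = 14 | g = 45 |
|---|---|---|---|---|
| Core Week 60 | 421 | 420/421 = 0.998 | 434/421 = 1.031 | 465/421 = 1.105 |
| Core Week 108 | 757 | 756/757 = 0.999 | 770/757 = 1.017 | 801/757 = 1.058 |
| Extension Week 240 | 2458 | 2457/2458 = 1.000 | 2471/2458 = 1.005 | 2502/2458 = 1.018 |

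Dividing 0.4 by these factors gives the loss since the scan at which the cut-off really acts. For g = 14 to 45 it is 0.388% to 0.362% per year at core Week 60, 0.393% to 0.378% at core Week 108 and 0.398% to 0.393% at extension Week 240.

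The Week 60 row assumes that the same clock is carried to that visit. The by-visit formula names extension scans only, so core Week 60 has no written annual formula, although NEDA-4 looks at any visit from core baseline.

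**Extension-only table at Week 48.** Time since the core EOT scan is 21 + 336 = 357 days, or 0.98 years. Two clocks used elsewhere in the SAP could be borrowed:

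- *Extension enrollment*, as for cumulative T2 lesions (5.3.1.2.2) and cumulative CUAL (5.3.1.2.3). With enrollment on Day 1 the clock is 337 days, and 357/337 = 1.06, so loss is overstated by about 6%. With consent 7 days before Day 1 the clock is 344 days, and 357/344 = 1.04. At Week 240, with enrollment on Day 1, the factor is 1701/1681 = 1.01.
- *Randomization*, as in the core-baseline formulas. The clock is 757 + 357 = 1114 days, or 3.05 years, and 357/1114 = 0.32. A subject would need to lose 0.4/0.32 = 1.25% per year to be counted. The factor is 693/1450 = 0.48 at Week 96 and 1701/2458 = 0.69 at Week 240.

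**The case against.** Randomization is the SAP's usual origin for combined-period time: study day (5.1.7.2), time to relapse (5.3.1.1.2), T2 lesions (5.3.1.2.2), CUAL (5.3.1.2.3) and CDA (5.3.1.3.2). One pre-specified origin, applied equally to both core treatment groups, is a defensible convention. Section 2 makes all analyses exploratory. The extension-only count does not feed NEDA-4, and Table 4 lists brain-volume change but not this threshold count. All of that stands and keeps the point small. It does not make randomization the better origin for a rate whose change is measured from a dated scan and judged against a fixed annual cut-off.

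A reader might infer two stronger things.

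- *That the rates feeding NEDA-4 are overstated as a matter of fact.* The document does not establish this. Section 5.1.3.2 allows a same-day scan, the interval is not stated, and the Visit 2 label comes from the text on T1 hypointense lesion volume.
- *That the extension-only table will understate loss threefold and hide real loss on ponesimod.* The document does not say so. The randomization formulas are labelled as changes from core baseline, and nothing assigns them to the core EOT table. The sibling MRI definitions point to extension enrollment, which errs slightly in the opposite direction.

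**Conclusion.** The point holds as a free improvement with a small effect on exploratory analyses. It has two separate parts.

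1. The core-baseline annual rates overstate loss to the extent that the baseline scan precedes randomization. Under an assumed lead of 14 to 45 days the overstatement is about 3% to 10% at core Week 60, 2% to 6% at core Week 108 and 0.5% to 2% at extension Week 240. With a same-day scan the +1 gives an understatement of at most about 0.2%. Only subjects close to -0.4% per year could change NEDA-4 status through this.
2. The count of annual change from core EOT has no defined rate or denominator. This is plain from the text and needs no assumption. The consequence depends on the clock chosen: about 6% overstatement at Week 48 with extension enrollment (21-day gap, enrollment on Day 1), or about threefold understatement with randomization, which is a worst case and not the expected outcome.

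Starting the clock at the reference scan is right whatever the unstated intervals are.

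**What to change.** In Section 5.3.1.2.4, define years of follow-up for every annual rate as (date of MRI - date of reference MRI)/365.25. The reference is the core baseline scan for changes from core baseline and the core EOT scan for changes from extension baseline. Add the variable annual percentage change from core EOT by visit, and point the second count in Section 5.3.2.3.4 to it. Word the by-visit core-baseline rate so that it also covers core scans, since NEDA-4 uses any visit.

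The cost is a few lines of SAP text and a short derivation change. It uses MRI scan dates already collected and needs no new data.

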5.3.2.4. Analysis of neurological variables

5.3.2.4.1. Analysis of disability progression (12/24-week CDA)

The analysis of time from core study baseline to confirmed first 12- and 24-week CDA will be summarized in a similar manner to the time to first relapse variable, for the Combined Analysis Period, using FAS and EXTS.

A listing with 12/24-week CDA results will be produced.

5.3.2.4.2. Change in EDSS from baseline by visit up to EOS

The EDSS score and change from baseline in EDSS score by visit and core study treatment group will be summarized using descriptive statistics on the EXTS for the Combined Analysis Period as well as on the EXTS for the Extension Analysis Period. Mean changes from core baseline in EDSS score are also presented graphically with their standard error over time (plots starting with zero change at baseline), for the Combined Analysis Period on the EXTS.

Analysis over the Extension Analysis Period will use the extension study baseline, whilst analysis over the Combined Analysis Period will use the core study baseline.

A listing(s) of EDSS / functional system (FS) scores will be produced.

5.3.2.5. Analysis of other efficacy variables

5.3.2.5.1. **NEDA-3** status up to **EOS**

Descriptive statistics of NEDA-3 status (Yes, No, Missing) up to Extension EOS including its components ([i] Presence of confirmed relapse, [ii] Presence of Gd+ T1 lesions, [iii] Presence of new or enlarging T2 lesions, [iv] 12-week CDA event, or [v] premature treatment discontinuation) will be presented using the EXTS. A listing will be prepared.

5.3.2.5.2. **NEDA-4** status up to EOS

NEDA-4 status up to Extension EOS will be analyzed in the same way as NEDA-3 status on the EXTS.

5.3.2.5.3. Change in MSFC Z-score from baseline by visit up to Extension EOS

MSFC Z-score as well as its subcomponents scores and changes from core baseline will be descriptively summarized for each treatment group by visit on the EXTS. Mean change (\pm SE) over time will be graphically presented by treatment group. Same analysis relative to extension baseline will be done on the EXTS during extension period. A listing will be prepared.

5.3.2.5.4. Change in the SDMT score from baseline by visit up to Extension EOS

SDMT scores and change from baseline will be descriptively summarized for each treatment group by visit on the EXTS. Mean change (\pm SE) over time will be graphically presented by treatment group. Same analysis relative to extension baseline will be done on the EXTS during extension period. A listing will be prepared.

5.4. Safety Analyses

All safety analyses will be based on the safety analysis set based on actual intervention received. Safety summaries for each analysis period will be based on the safety analysis sets described in Section 4, unless otherwise specified.

For all continuous safety variables, descriptive statistics by intervention group will include the N, mean, standard deviation, median, minimum, and maximum. To convey the uncertainty associated with the summary statistics, the line plots will incorporate standard error (defined as sample standard deviation divided by the square root of sample size) for continuous variables. Categorical variables will be summarized by intervention group using frequency counts and percentages.

5.4.1. Extent of Exposure

5.4.1.1. Definition of extent of exposure

5.4.1.1.1. Exposure (Time on treatment)

The following variables are defined for exposure during the Extension Analysis Period:

Duration of exposure to ponesimod in the extension (months) excluding interruptions is defined as the time elapsed between (the date of first study drug intake in the extension study and date of last study drug intake in the extension study $+ 1 \times 12 / 365.25$, excluding any temporary treatment interruptions.

Duration of exposure to ponesimod in the extension (months) is defined as the time elapsed between (the date of first study drug intake in the extension study and the date of last study drug intake in the extension study $+ 1 \times 12 / 365.25$, independent of any treatment interruptions (except for treatment interruption due to planned pregnancy).

In addition, the duration of exposure as derived above for each subject is categorized as follows:

- > 1 day and < 6 months;
- > 6 months and ≤ 12 months;
- > 12 months and < 18 months;
- > 18 months and ≤ 24 months;
- > 24 months and ≤ 30 months;
- > 30 months and ≤ 36 months;
- > 36 months and < 42 months:
- > 42 months and < 48 months;
- > 48 months and \leq 54 months;
- > 54 months and < 60 months;
- > 60 months.

The following variables are defined for exposure to ponesimod treatment during the **Combined Analysis Period**, for subjects randomized to ponesimod in the core study only:

Combined duration of exposure to ponesimod (months) excluding interruptions is defined as the time elapsed between [the date of first ponesimod intake in the core study and the date of last

ponesimod intake in the extension study + 1 (in days)] $\times 12 / 365.25$, excluding any temporary treatment interruptions.

Combined duration of exposure to ponesimod (months) is defined as the time elapsed between [the date of first ponesimod intake in the core study and the date of last ponesimod intake in the extension study + 1 (in days)] $\times 12 / 365.25$, independent of any treatment interruptions (except for treatment interruption due to planned pregnancy).

In addition, the combined duration of exposure for each subject is categorized as follows:

- ≥ 1 day and ≤ 6 months;
- > 6 months and ≤ 12 months;
- > 12months and < 18 months;
- > 18 months and ≤ 24 months;
- > 24 months and ≤ 30 months;
- > 30 months and ≤ 36 months;
- > 36 months and \leq 42 months;
- > 42 months and \leq 48 months;
- > 48 months and \leq 54 months;
- > 54 months and \leq 60 months;
- > 60 months and \leq 66 months;
- > 66 months and \leq 72 months;
- > 72 months and ≤ 78 months;
- > 78 months and ≤ 84 months
- > 84 months

5.4.1.1.2. Compliance with study treatment

Compliance is calculated as a percentage as:

Ponesimod exposure during the Analysis Period excluding interruptions / Ponesimod exposure during the Analysis Period independent of interruptions (except for treatment interruption due to planned pregnancy as defined above) \times 100.

Compliance as derived above is categorized as $< 80\%, \ge 80 - < 90\%, \ge 90 - < 95\%, \ge 95 - < 100\%, 100\% and > 100\%.$

5.4.1.1.3. Treatment duration (days with intake documented) during up-titration period (extension study)

The number of days with intake documented is based on entries on the eCRF 'Up-titration Summary' and/or 'Up-titration Ponesimod'.

For subjects where the investigator confirmed the up-titration has been conducted as planned, the 'Up-titration Summary' eCRF is filled out, collecting only start and end date of the entire titration period without collecting 'number of tablets taken'. In that case the 'Number of days with intake documented' is derived and considered to be 'titration end date - titration start date + 1 day'.

For all other subjects, information is collected on the 'Up-titration Ponesimod' eCRF, 'Intake date' resulting in potentially multiple records of up-titration drug intake (collecting in addition 'number

of tablets taken'). In that case, 'Number of days with intake documented' for each record is derived in the same way as during the maintenance period.

5.4.1.1.4. Treatment duration (days with intake documented) during maintenance period (extension study)

Per protocol, one tablet of study drug is to be taken per day. On the 'Maintenance Ponesimod' eCRF log form, each record collects 'Treatment start date', 'Treatment end date', 'Daily Dose' (Default value 20 mg – Maintenance), and 'Total number of tablets taken'. If, for a record, the 'Number of tablets taken' is \leq 'Treatment end date' – 'Treatment start date' + 1, it is assumed that the 'Number of tablets taken' represents the 'Number of days with intake documented' during that record's period of study drug intake. If, for a record, the 'Number of tablets taken' is > 'Treatment end date' – 'Treatment start date' + 1, 'Number of days with intake documented' is set to 'Treatment end date' – 'Treatment start date' + 1. These subjects are flagged as having taken > 1 capsule per day on at least one occasion.

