5.4.1.1.6. Study treatment interruptions

Study treatment interruptions in the core study is used as derived in the core study.

Temporary treatment interruptions refer to any period of time between a temporary study treatment end date and subsequent study treatment start date during which the subject did not receive study treatment. When considering the Combined Analysis Period, the time between end of treatment in the core study and start of treatment in the extension study is also a treatment interruption. The cumulative duration of all such treatment interruptions is derived for each subject.

In addition, for each subject, the number of interruptions > 3 days is counted.

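### Extension-period compliance is a date-gap ratio: tablets missed inside a dosing record never lower it, and its > 100% category cannot be reached

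*SAP*

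**What the plan says.** Section 5.4.1.1.2 sets compliance, as a percentage, to "Ponesimod exposure during the Analysis Period excluding interruptions / Ponesimod exposure during the Analysis Period independent of interruptions", with planned-pregnancy interruption taken out. Section 5.4.1.1.1 builds both terms from the first and last intake dates. The numerator differs only in "excluding any temporary treatment interruptions". Section 5.4.1.1.6 defines the quantity removed: "Temporary treatment interruptions refer to any period of time between a temporary study treatment end date and subsequent study treatment start date". For the Combined Analysis Period that section also counts the time between core and extension treatment as an interruption.

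Section 5.4.1.1.2 then bands the result ("Compliance as derived above is categorized as" introduces the list), from below 80% up to exactly 100% and above 100%.

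Two neighbouring sections, both limited to the extension study, derive a different quantity, the days with documented intake:

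- Maintenance (5.4.1.1.4): "Per protocol, one tablet of study drug is to be taken per day". Where the tablet count does not exceed the record length, "it is assumed that the 'Number of tablets taken' represents the 'Number of days with intake documented' during that record's period". A larger count is capped at the record length and the subject is flagged.
- Up-titration (5.4.1.1.3): if done as planned, the form works by "collecting only start and end date of the entire titration period without collecting 'number of tablets taken", so intake days are the date span. Otherwise tablets are recorded and treated as in maintenance.

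Compliance is tabulated for both analysis periods (5.4.1.2.2), before and after 1 January 2020 (5.5.9), and before and after 24 February 2022 (5.5.10). Appendix 7 states that no compliance calculation applies to this study.

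**The concern.** A compliance percentage is normally read as the share of scheduled doses taken. This one is the share of the treatment span not covered by a logged stop. The two agree only if every missed day is recorded by closing one dosing record and opening another. The SAP derives an intake measure that does not depend on this, and then uses it neither in the compliance formula nor in the exposure summaries of 5.4.1.2.1.

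The categories suggest that formula and table were not designed together. A ratio whose numerator is its denominator minus something cannot exceed 100%; a tablet-count ratio can.

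At stake is how the compliance tables are read. Subjects who missed many tablets could sit in the 100% row. In the Covid-19 and regional-crisis tables, reduced intake without a logged stop would leave no trace.

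**Working it through.** The SAP gives no compliance figure, so there is none to reproduce. The check applies its definitions to constructed cases.

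**Inputs**
- Span D = 240 weeks × 7 = 1680 days (planned extension treatment, section 1.2.3), without planned pregnancy.
- G = total days in logged gaps (5.4.1.1.6).
- T = tablets taken, one expected per day (5.4.1.1.4).
- m = share of tablets missed. This is an assumption; the SAP gives no value.

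**Formulas**
- SAP: C_date = 100 × (D − G) / D. The months conversion in 5.4.1.1.1 cancels.
- Tablet-based, one record: C_tab = 100 × min(T, D) / D, using the cap in 5.4.1.1.4.

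**Tablets missed inside one record, G = 0**

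| m (assumed) | T | C_date | C_tab |
|---|---|---|---|
| 0% | 1680 | 100% | 100% |
| 5% | 1596 | 100% | 95% |
| 10% | 1512 | 100% | 90% |
| 20% | 1344 | 100% | 80% |
| 30% | 1176 | 100% | 70% |

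C_date does not contain T, so the first result column is constant. Splitting the period into several contiguous records changes nothing, because G stays 0.

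**Same 168 days without drug, recorded two ways**
- Logged as a stop and restart: C_date = 100 × (1680 − 168) / 1680 = 90.0%.
- Missed inside one open record: C_date = 100 × 1680 / 1680 = 100.0%.
- C_tab = 100 × 1512 / 1680 = 90.0% in both cases.

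**Category above 100%**
- Since G ≥ 0, C_date ≤ 100%. With 1700 tablets in 1680 days, C_date = 100.0%. The capped C_tab is also 100.0%. Only the uncapped count exceeds it: 100 × 1700 / 1680 = 101.2%.

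**Combined Analysis Period**
- Here the core-to-extension gap is part of G. With 108 × 7 = 756 core days, 1680 extension days and an assumed gap of 14 to 44 days, the most a subject who entered the extension can score is 100 × 2436 / 2450 = 99.4% to 100 × 2436 / 2480 = 98.2%. The result of 100% without logged gaps therefore belongs to the Extension Analysis Period.

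**The case against.** The strongest reply has four parts.

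- **Real stops are captured.** The SAP counts interruptions longer than 3 days, flags those without a new up-titration, and counts those with one as re-initiations. Section 5.4.1.2.1 also reports the number and cumulative duration of interruptions. Hundreds of tablets missed within one open record would mean that stops went unrecorded, so what is most clearly lost is scattered single doses. This stands as a limit on the likely size. It does not change what the formula measures.
- **The tablet data do not reach everywhere.** Documented-intake days are defined here for the extension only, and an up-titration done as planned has no tablet count. Tablets are one total per record, so a record spanning 1 January 2020 or 24 February 2022 cannot be divided without an assumption, whereas dated gaps can. This stands and shapes the fix.
- **Little depends on it.** The study is open-label and non-comparative, and all analyses are exploratory. Compliance defines no analysis set and enters no efficacy or safety estimate. This stands.
- **An interruption-based ratio is a legitimate choice.** It is, under a name that says so. The unreachable category and the contradiction with Appendix 7 would still need correcting.

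A reader might infer that reported compliance is in fact overstated by 5 to 30 points. The documents do not support that: those shares are assumptions, and the true rate could be near zero. A reader might also infer that all inputs for a tablet-based measure are already in hand. That is not so for the core study or for records spanning a cut date.

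**Conclusion.** The point holds for the Extension Analysis Period. By the SAP's own definitions, compliance there cannot fall because of tablets missed between a record's start and end dates, and its top category cannot be filled. For a subject without logged gaps, the difference from a tablet-based figure equals the missed share, in percentage points. How large that is in this study cannot be judged from the SAP.

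The conclusion assumes that interruption means what 5.4.1.1.6 says, a gap between recorded dates. If a tablet-based reading was intended, the text needs correcting to say so. The effect is confined to descriptive compliance tables. It is worth correcting before they are produced, but no efficacy or safety result changes.

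**What to change.** 1. **Extension Analysis Period (5.4.1.1.2, 5.4.1.2.2).** Define compliance as 100 × (sum of documented-intake days from 5.4.1.1.3 and 5.4.1.1.4) / (exposure days excluding planned-pregnancy interruption). State that up-titration done as planned contributes its date span.
2. **Date-gap ratio.** Keep it under a separate name, such as percentage of treatment time without logged interruption. Use it for the Combined Analysis Period unless intake days can be taken from the core derivations.
3. **Sections 5.5.9 and 5.5.10.** Use the tablet-based measure only with a stated rule for records spanning the cut date, for example allocation pro rata by days. Pro rata gives both sides of a spanning record the same intake rate, so such a record cannot itself show a change; report how many there are. Without a rule, label these tables as interruption-based.
4. **Categories.** Delete the one above 100%, or base it on uncapped tablet counts. With capped intake days it stays empty.
5. **Appendix 7.** Reconcile it with the sections that do calculate compliance.

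The cost is SAP wording and modest programming, with no new data collection. Item 1 uses variables the SAP already derives; item 3 needs an allocation rule and its programming. Reported extension compliance may be somewhat lower.
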